10.0 PHARMACOKINETIC ANALYSES

Blood samples for PK evaluations will be collected as per SOE. PK disposition of CAP256V2LS and VRC07-523LS will be evaluated in this study and described in the SAP. PK assessments will be conducted retrospectively on stored samples for all HIV seroconvertors and a sub-set of participants at a minimum of two timepoints. PK profiles between the different groups will be analysed as per SAP. CAP256V2LS and VRC07-523LS systemic and mucosal concentrations in relation to breakthrough infections will also be evaluated. Summary descriptive results of PK parameters will be reported. PK parameters will be calculated using standard non-compartmental methods; C_{max} and T_{max} taken directly from the data, area under the curve (AUC) the trapezoidal method up to the last concentration and terminal half-life from regression of the log-linear, terminal portion of the concentration versus time profile. A population PK analysis will be performed using a two-compartment model and the computer program NONMEM, version 7.3 or later.

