three doses of either 20 mg/kg intravenous VRC07-523LS, or 5 mg/kg subcutaneous VRC07-523LS at 12-week intervals. There were no safety concerns with favourable PK reported. VRC07-523LS had an elimination half-life of 38 days for the IV groups and 33 days for SC groups. Sera containing VRC07-523LS displayed equivalent or greater neutralisation activity than those containing VRC01 or VRC01LS from previous trials.

Rationale for trial design amendment

Assessment of Preliminary CAPRISA 012B phase 1 PK data indicates that concentrations above the 1mcg/ml 'target' concentration is achievable for doses above 10mg/kg for both CAP256V2LS and VRC07-523LS, consistently maintained over 168 days after a single subcutaneous administration (Figure 2). The study products CAP256V2LS and VRC07-523LS are available in 6ml vials and contain 600mg of antibody per vial. We propose an initial fixed dose of 1200mg of both VRC07-523LS and CAP256V2LS which equates to 2 vials of each bnAb used per participant, followed by a 6-month dosing interval of 1200mg (2 vials) of VRC07-523LS and 600mg (1 vial) of CAP256V2LS. This dosing strategy is based on a recent analysis (*Gilbert P et al, Neutralization titer biomarker for antibody-mediated prevention of HIV-1 acquisition. Nature Medicine. 2022 Sep;28(9):1924-32*) that estimates concentrations of bnAbs required for protection. When applied across a range of weights this dose is adequate to reach well beyond the target concentration, example: 1200mg translates to a dose of 20mg/kg for a 60kg person, 15mg/kg for a 90kg person and 10mg/kg for a 120kg person.

[figure not shown]

Figure 2: Median CAP256V2LS and VRC07-523LS over 168 days from the CAPRISA 012B phase 1 trial.

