3.5 Secondary endpoints

- Documented HIV-1 infection during follow up
- Differences in the PK profile of study products administered 16 weekly (4 monthly) in comparison to 24 weekly (6 monthly) administration
- Differences in the PK profile of study products administered as weight-based dosing in comparison to fixed dosing.
- Changes in the concentration of systemic and mucosal concentrations of CAP256V2LS and VRC07-523LS titres in breakthrough infections
- Proportion of participants reporting CAP256V2LS injections to be acceptable as per study questionnaire

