5.10 Follow-up visits

All follow up visits will take place as per the SOE. For all participants, reactogenicity assessments are performed before (baseline) and after each study product administration as per the SSP. A reactogenicity assessment will be conducted at the clinical site on Day 0, approximately 60 minutes post study product administration. In addition, all participants will be asked to keep a daily diary of local and systemic symptoms for 3 days after each product administration. All participants will be counselled on the expected reactogenicity events and on how to record these events. Participants will also be asked to record their temperature daily from Day 0 to Day 3.

A virtual visit will be conducted by study staff on Day 3 and Day 7 post study product administration or sooner if indicated. In this protocol, a virtual visit refers to any remote or web-based consult with a participant and includes but is not limited to telephonic communication, email communication, messaging, video calls or web applications. At these virtual visits, study staff will discuss reactogenicity events and/or adverse events with the participant and record the relevant information on either the appropriate CRF(s) or participant chart note as per SSP. Clinic staff will follow new or unresolved reactogenicity symptoms present at day 3 to resolution. In general, a participant who self-reports any event greater than moderate and/or requires medical intervention is seen by a clinician within 48 hours after onset, unless the reaction is improving and/or has completely resolved.

All laboratory tests will take place as per the SOE. The total blood volume drawn from each participant will comply with regulatory guidelines. Additional assessments of health and/or laboratory tests may be conducted at follow up visits based on clinical judgement. Laboratory test(s) may be repeated at the discretion of the PI or designee.

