Appendix 1. Part A: Group 1a/1c Schedule of Evaluations (4 monthly)

Product Administration Phase												Study Exit	
Study Month	SCR	M0			M2	M4			M6	M8		M10	M12
Study Week		W0				W16				W32			
Virtual Visit (1)			VV1	VV2			VV3	VV4			VV5	VV6	
Study Day (post study product/placebo)		D0	D3	D7		D0	D3	D7		D0	D3	D7	
Study Product/ Placebo administration		X				X				X			
Administrative, Behavioural and Regulatory Procedures													
Informed consent for study participation	X												
Comprehension assessment	X	X											
PID assignment	X												
Eligibility assessment (2)	X	X				X				X			
Locator information	X	X			X	X			X	X		X	X
Demographic information	X												
Randomisation		X											
Behavioural Assessment	X	X			X	X			X	X		X	X
Risk Reduction counselling	X	X			X	X			X	X		X	X
HIV-test Counselling (3)	X	X			X	X			X	X		X	X
Contraceptive counselling and provision (4)	X	X			X	X			X	X		X	X
Product acceptability assessment		X				X				X			
Clinical Procedures													
Comprehensive Medical History	X												
Interim Medical History		X	X	X	X	X	X	X	X	X	X	X	X
Concomitant Medications	X	X	X	X	X	X	X	X	X	X	X	X	X
Comprehensive Physical Exam	X												
Targeted Physical Exam		X			X	X			X	X		X	X
Weight	X	X			X	X			X	X		X	X
Height	X												
Vital Signs	X	X			X	X			X	X		X	X
Reactogenicity Assessment (5)		X	X	X		X	X	X		X	X	X	
Adverse Events		X	X	X	X	X	X	X	X	X	X	X	X
Clinical Laboratory Tests (6)													
Full Blood Count, differential	X	X				X				X			
ALT, creatinine	X	X				X				X			
Pregnancy test (7)	X	X			X	X			X	X		X	X
HIV testing (8)	X	X			X	X			X	X		X	X
Storage (6)													
Plasma Storage	X	X				X				X			X
Serum Storage	X	X				X				X			X
Pharmacokinetics sampling (9)	X	X			X	X			X	X		X	X
Genital mucosal sampling (10)		X				X							
PBMCs		X											X

1. Refers to any remote consult with a participant as described in the protocol and SSP.

2. Eligibility to enrol into the study will be assessed before the first study product administration and eligibility to receive study product will be assessed thereafter

3. Includes pre-test counseling and post-test counseling as indicated. A subsequent follow-up contact may be conducted to provide post-test counseling and to report results to participant.

4. Conducted when clinically indicated

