5. Reactogenicity assessments performed at approximately 60 minutes post study product administration and via virtual visit three days post study product administration as per protocol. If required, this information will be updated on Day 7 virtual visit.

6. Total blood volume collection will not exceed 500 ml within 6 weeks

7. May include urine or serum pregnancy test as clinically indicated

8. HIV testing will be conducted as per an HIV testing algorithm described in the SSP

9. PK assessments will be conducted retrospectively on stored samples for all HIV seroconvertors and a sub-set of participants at a minimum of two timepoints

10. Genital mucosal sampling will include cytobrushes, genital swab/s and/or Softcup.

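### Non-compartmental Cmax, Tmax and AUC cannot be obtained from a schedule with no PK sample before week 8 or week 12, and between the 16- and 24-weekly groups they would differ because of the visit calendar

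*Protocol*

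**What the plan says.** Protocol section 10.0 states "Blood samples for PK evaluations will be collected as per SOE". It then sets out a non-compartmental analysis. The peak and the time of the peak are to be "taken directly from the data, area under the curve (AUC) the trapezoidal method up to the last concentration". For the half-life, a line is to be fitted to the log concentrations in the last part of each profile. The same section plans a two-compartment population PK analysis and leaves the analysis of PK profiles between groups to the SAP.

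The sampling times are in the appendices:

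- Appendix 1 (16-weekly, doses at weeks 0, 16 and 32) marks PK blood at the clinic visits only: screening, M0, M2, M4, M6, M8, M10 and M12.
- Appendix 2 (24-weekly, doses at weeks 0 and 24) marks it at screening, M0, M3, M6, M9 and M12.
- Appendix 3 (Part B) also follows 3-monthly clinic visits.

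The contacts soon after dosing carry no PK mark. Section 5.10 says "A virtual visit will be conducted by study staff on Day 3 and Day 7 post study product administration" and defines a virtual visit as a remote consultation. The footnote to the PK row adds: "PK assessments will be conducted retrospectively on stored samples for all HIV seroconvertors and a sub-set of participants at a minimum of two timepoints".

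A secondary endpoint in section 3.5 is "Differences in the PK profile of study products administered 16 weekly (4 monthly) in comparison to 24 weekly (6 monthly) administration". Table 2 gives both Part A antibody groups 20 mg/kg of each antibody.

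**The concern.** The parameter definitions and the sampling schedule do not fit each other. A Cmax read off the data is a peak only if someone samples near the peak. Here the first informative sample after a dose comes about 8 weeks later in one group and about 12 weeks later in the other, with one more sample before the next dose. The observed maximum is simply the first of these two values, and the observed Tmax is the day of that visit. The trapezoid runs in a straight line from the dosing-day value to that first sample and so cuts off the peak.

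The loss is not equal in the two groups. The longer wait in the 24-weekly group lowers its apparent peak and AUC further, so the reported parameters would show a regimen difference that comes from the visit dates. That falls on a stated secondary endpoint.

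**Working it through.** The protocol gives no figure for the PK comparison, so there is nothing to reproduce. The check applies the section 10.0 rules to two groups with identical true pharmacokinetics.

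**Inputs**
- Sampling days, from Appendices 1 and 2: 0, 56, 112, … 336 (16-weekly); 0, 84, 168, 252, 336 (24-weekly).
- Dosing-day samples taken as pre-dose. This is an assumption, since the protocol does not say. A sample about an hour after a subcutaneous injection would not capture the peak either.
- Half-life: section 2.6.2 says "VRC07-523LS had an elimination half-life of 38 days for the IV groups and 33 days for SC groups". The 33 days are used, with an assumed range of 20 to 50 days, because the documents give no human half-life for CAP256V2LS.
- True Tmax: assumed 3 to 14 days. The documents give no human subcutaneous value.
- Model: one compartment, first-order absorption, C(t) ∝ exp(−ke·t) − exp(−ka·t), with ke = ln 2/33 = 0.0210 per day and ka solved for the assumed Tmax.

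**Cmax and Tmax, first dose**
1. Once absorption is over, the ratio of the first samples depends only on the 28-day gap between them: 2^(28/33) = 1.80. The true ratio is 1.00. At a 20-day half-life it is 2^(28/20) = 2.64; at 50 days, 2^(28/50) = 1.47.
2. The observed Cmax is 33 to 47% of the true peak in the 16-weekly group and 19 to 26% in the 24-weekly group (Tmax 3 to 14 days).
3. The observed Tmax is 56 versus 84 days, whatever the true value.

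**AUC, first interval (Tmax 7 days, amounts per unit dose)**
1. 16-weekly: C(56) = 0.3231 and C(112) = 0.0997. Trapezoid = 56 × 0.3231/2 + 56 × (0.3231 + 0.0997)/2 = 20.88. The true AUC is 42.86, so 49% is recovered.
2. 24-weekly: C(84) = 0.1794 and C(168) = 0.0307. Trapezoid = 84 × 0.1794/2 + 84 × (0.1794 + 0.0307)/2 = 16.36. The true AUC is 46.15, so 35% is recovered.
3. Over Tmax 3 to 14 days, recovery is 47 to 54% versus 34 to 39%.

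**AUC over the 12-month schedule, ratio 16-/24-weekly**

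| Half-life | Observed | True |
|---|---|---|
| 20 days | 2.87 | 1.49 |
| 33 days | 2.11 | 1.47 |
| 50 days | 1.82 | 1.44 |

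**Half-life**
1. Without noise, two points in the terminal phase return 33 days on either calendar, so there is no calendar bias.
2. Two points leave no residual degrees of freedom. With an assumed 20% CV per sample, the log-scale SD is √ln(1.04) = 0.198 and the SE of the slope is √2 × 0.198/gap. The 95% range for one participant is about 22 to 62 days (56-day gap) and 25 to 48 days (84-day gap).

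**The case against.** The strongest defence is that section 10.0 leaves the between-group method to the SAP, offers the non-compartmental parameters as descriptive summaries, and plans a population PK model that uses actual times since dose. All of that is true, and it lowers the weight of the point. It does not remove it. The definitions and the sampling times are both fixed in the protocol, the parameters are to be reported, and no later choice of test repairs values that miss the peak.

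A reader might also infer four stronger things that the documents do not support.

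- *That half-life is distorted by the calendar.* It is not, if decline is log-linear after week 8. It is only imprecise. After the last Part B dose, the off-product follow-up described in the Appendix 3 footnote allows more than two samples.
- *That the weight-based versus fixed-dose endpoint suffers the same offset.* Set against the 24-weekly Part A group, Part B shares the 3-monthly calendar. Cmax, Tmax and AUC still miss the peak there, but without an offset between groups.
- *That the AUC comparison points the wrong way.* This happens only for the first interval: at 33 days the ratio is 20.88/16.36 = 1.28 observed against 42.86/46.15 = 0.93 true. It persists at 50 days (1.05 against 0.87) but is gone at 60 days (0.98 against 0.85). Section 10.0 does not limit AUC to the first interval, and over 12 months the ratio is inflated in the right direction.
- *That the phase III dose and interval would be chosen on these parameters.* Section 2.3 names antibody concentrations and breakthrough infections, not Cmax or AUC. Observed concentrations remain usable.

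**Conclusion.** The point holds for Cmax, Tmax and trapezoidal AUC. On the Part A schedules they cannot describe peak or total exposure, and between the 16- and 24-weekly groups they carry a difference created by the visit dates. The Tmax result follows from the schedule alone. The sizes in the working rest on a one-compartment model, a half-life taken from one of the two antibodies, and an assumed Tmax. Across the assumed half-lives the false first-dose Cmax ratio stays well above 1, and the 12-month AUC ratio stays above its true value.

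This should be corrected, but it does not block the trial. The endpoint is secondary, the comparison method is still open to the SAP, and a suitable model is already planned.

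**What to change.** In section 10.0, drop non-compartmental Cmax, Tmax and AUC for this schedule. Base the 16- versus 24-weekly comparison on:

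- observed troughs, stated to be drawn before the injection where they fall on a dosing day, each labelled with its time since dose;
- concentrations at matched times since dose. The Part A groups are sampled at 8 and 16 weeks versus 12 and 24 weeks and share no nominal time, so these must come from the model;
- AUC, average concentration and half-life from the planned population PK model, with absorption and distribution parameters fixed at, or given priors from, the sponsor's phase I data.

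Keep any regression half-life as descriptive only.

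This changes wording and needs no new samples. The price is that peak and absorption would rest on phase I information, because this trial's own data say almost nothing about them before week 8. If the sponsor wants observed peaks from this trial, the alternative is early post-dose samples in a sub-set, at the same times in both regimens, at the cost of extra clinic visits and blood draws.

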11.0 DATA MANAGEMENT

All data management activities will be undertaken under the applicable regulatory frameworks. This includes the U.S Food and Drug Administration (FDA) regulations, European Medicines Agency (EMA) regulations and the regulatory agencies in South Africa and Zambia. All studies will also abide by the local Ethics Committee (EC) regulations. The Data management systems in CAPRISA and CIDRZ meet FDA requirements as they are CFR Part 11 compliant. The Data Management standard processes are aligned with the Good Clinical Data Management Processes (GCDMP). Data collection for this study at each site will involve one of two methods or a hybrid method where both systems can be used simultaneously based on each site's capabilities or preferences:

Paper based method

Data will be collected on case report forms (CRFs) which will be developed by the study team. All site study staff will be trained on the correct completion of CRFs. If data entered on the CRFs are taken from an external source (e.g., laboratory reports, participant records), the source documents will be maintained in the participant's medical chart or study file at the site and will be available for review. The CRFs will be scanned into the database management system which is DFdiscover 2018 Version 5.1. DFdiscover has optical character recognition (OCR) which reads the check boxes and numerical fields on the CRFs and stores them in the study database. Any fields not recognized by the OCR system will be entered manually by the data encoders. Data encoders will verify all data by cross-checking the scanned version to what is entered into the database.

Queries arising during validation of the data will be recorded in quality control (QC) reports and sent to the sites on a regular basis. Any queries resulting in a change to the database will be documented on the original CRF and re-scanned. The data management centre staff will perform periodic quality control and validation checks on the data. Database files will be password-protected and access to the files will be limited to authorised study staff members only.

Electronic Data Capture (EDC)

DFdiscover (5.1.4, DF/Net, Seattle, USA) will be used for electronic data capturing.

DFdiscover is a validated clinical database management system which is FDA CFR Part 11 compliant. Electronic Case Report Form (eCRF) data will reside on the DFdiscover server housed at CAPRISA Doris Duke Medical Research Institute and is backed up at regular intervals by CAPRISA and securely stored at CAPRISA Doris Duke Medical Research Institute and the other at the eThekwini research clinic.

The electronic-CRF design will be guided by the study protocol with final approval by the study team and the PI. All study staff will be allocated user roles, specific to their function required for data entry. Database access will be restricted by passwords and permission levels. The study staff and statistician can access the database in “read-only” mode once data has been entered. The CAPRISA data management team will have write-access. In the event of internet downtime, power outages, or any situation that makes the DFdiscover system inaccessible, one-ply paper CRFs will be used to collect the data, which will be scanned through to the CAPRISA data centre once the internet is active again.

General data management

All study CRFs and related documents will be stored securely both during and after study completion. During the study, the original completed forms for each participant will be kept on-site at the respective sites. The forms will be stored in a secured, double-locked, fire-resistant and waterproof bulk storage filer. Upon completion of the study, and finalization of the database for analysis, the original forms will be bound and kept off-site (separate site) for long-term storage. CRF data on the DFdiscover server, housed by CAPRISA at Doris Duke Medical Research Institute and backed up at CAPRISA’s eThekwini research site, will be accessible to the study staff and the statistician in a view-only mode. The data management team will have write-access, with access being restricted by passwords and permission levels. Study staff that has access to the data on the computer will be trained on how to access the system and the importance of system security.

All queries and/or reasons for data changes will be generated electronically and will form part of the weekly QC Report that will be distributed to the appropriate study team members. Study staff also have the option of addressing any query at any time. Queries arising during validation of the data will be recorded in quality control (QC) reports sent to the sites on a regular basis. QC rates will be communicated to the site monthly. Monthly data downloads will be sent to the study statistician. These data downloads will also be made available on request. Study staff who have access to the data on their computer systems will be trained on how to use the system and the importance of system security. Support will always be available from the data manager and IT department at CAPRISA, if any issues arise.

For staff who need to access DFdiscover remotely (external organisations that are part of the study), the client software will be installed remotely by the data management team. The same security settings as CAPRISA site will apply to all external sites accessing DFdiscover. All CRFs and source documents are to be securely stored in the participant study file in a secure double-locked, fire resistant unit with restricted access in accordance with GCP requirements. Upon completion of the study, the close-out site monitoring visit and finalization of the database for analysis, any original forms will be bound and kept for long term storage. Study documentation and CRFs will not be destroyed without written permission from the sponsor.

11.1 Data Sharing

All study team scientists will disseminate the trial results as broadly as possible. The study data will be published consistent with normal scientific practices. Research data that document, support, and validate research findings will be made available after the main findings from the final research dataset have been accepted for publication. Such research data will be modified to prevent the disclosure of personal identifiers to remain in compliance with the Protection of Human Subjects. The research team will attend conferences periodically and present trial results to a multidisciplinary scientific community. The results from this research may also be disseminated through presentations at scientific institutions/meetings, and/or publication in scientific journals. All publications will be uploaded to the UKZN publication repository. After sharing the results with study participants, they will be presented to communities from which participants are recruited, following Good Participatory Practice guidelines. The results will also be shared with global and local policy makers. Summary results of the trial will be made publicly available through the clinical trial registry. Any datasets used for analysis in publications can be requested by investigators via an online request to the organisation. Measures will be taken to protect identifiable information in the datasets. A detailed communication plan will be developed specifically for this study. This communication plan will be in place to address the six major types of stakeholders for HIV prevention trials. These include the clinical research enterprise, individual users, community members, advocates and policy makers, and program implementers.

